## AE end dates

- If Day only is missing, incomplete end dates will be replaced by the last day of the month, if not resulting in a date later than the date of the subject's death or date of study discontinuation. In the latter case, the date of death/date of study discontinuation will be used to impute the incomplete end date.
- If Day & Month are missing, Day & Month will be replaced by 31DEC, if not resulting in a date later than the date of the subject's death or date of study discontinuation. In the latter case, the date of death/ date of study discontinuation will be used to impute the incomplete end date.
- In all other cases the incomplete end date will not be imputed.

## **Concomitant Medications dates**

Partially missing dates for prior and concomitant medications and procedures will be imputed. Of note, imputation of missing/partial dates will be done only to identify the treatment period assignment.

- End date: Missing day will be imputed as the last day of the month, and missing month will be imputed by December, if not resulting in a date later than the date of the subject's death or date

Sponsor:	ObsEva		
Protocol:	19-OBE2109-005		
Document Version No.:	1.0	Document Date:	18-MAY-2021

of study discontinuation In the latter case, the date of death/date of study discontinuation will be used to impute the incomplete end date.

- Start date: Missing day will be imputed as the first day of the month, and missing month will be imputed by January.
- If the start date is completely missing, then:
  - If the end date is prior to the date of first administration of the study drug, then the medication is considered as prior
  - If the end date is prior to the date of last administration of the study drug, then the medication is considered as prior and concomitant
  - If the end date is completely missing or after the date of last administration of the study drug, then the medication is considered as prior, concomitant and post.

Following imputation of the dates, the concomitant medications will be assigned to the main study and/or the extension study according to imputed start and end dates. Note that a concomitant medication starts before the first IMP administration in the main study and stops during the extension study will be assigned to both studies.

## 4.2.8.2. eDiary Devices Data Cleaning

Due to eDiary system errors, mapping rules are defined for data cleaning, as described in Appendix E in Section 7.1.

In addition, the following rules are defined for handling of duplicate records:

- A change of eDiary device vendor ( vendor to Signant Health vendor) occurred during the study.
- Some subjects may have entered data in the two different devices during the transition period. In case of duplicates results on the same day for daily diaries or on the same visit for monthly questionnaires, data from the new vendor (Signant Health) will be used for analysis.
- In case of duplicates within the same device, the first record (with earliest date/time) should be used for analysis.

Additional rules to specific e-diary domains will be applied:

Analgesic use data:

- Analgesic use data from "Today" will be used primarily. If data from "Today" is missing, data from "Yesterday" of the following day will be considered

CRS-BS-TP-000005 V 1.0

#### Page 29 of 66

# Cytel

## Statistical Analysis Plan

Sponsor:	ObsEva		
Protocol:	19-OBE2109-005		
Document Version No.:	1.0	Document Date:	18-MAY-2021

IMP Intake Data:

- IMP Intake data from "Today" will be used primarily. If data from "Today" is missing, data from "Yesterday" of the following day will be considered

## device specific rules

NOTE: by design, when a subject is completing a questionnaire (daily or monthly) on a device, the device automatically saves all answers provided by the subject as soon as recorded, unless subject uses the "previous" button to come back to already answered question(s) within the questionnaire and changes her answer(s) prior to finishing the questionnaire.

There are several triggering questions in the study questionnaires: the next question(s) to be presented to the subject will depend on the answer chosen by the subject to the current question.

Due to device functioning, when an answer to a triggering question has been changed by subject (using previous button), the device keeps subsequent answer(s) to the previously triggered question(s), even if this/these question(s) is/are no longer relevant considering the new answer to the triggering question.

The agreed rules consider the last entry made by the subject i.e. the entry that would have not allowed her to provide additional data or to modify data for the sub-questions (in contrast to the **section** device, with the Signant Health device, the intermediate answers are not saved and will not be present in the database; the agreed rules are aligned with this functioning).

Analgesic use data:

- If answer to question "Did you take any provided/prescribed analgesic for your endometriosis related pain?" is "Yes" or empty but the number of ibuprofen intakes and narcotic analgesics intakes are both 0, it will be considered that no analgesic was used on that day.
- If answer to question "Did you take any provided/prescribed analgesic for your endometriosis related pain?" is "Yes" or empty, but question to Ibuprofen intake is "No" and the number of ibuprofen intakes is not zero, it will be considered that no ibuprofen was used on that day. The same rule will be applied for narcotic analgesics.
- If answer to question "Did you take any provided/prescribed analgesic for your endometriosis related pain?" is "No" and the number of ibuprofen intakes and narcotic analgesics intakes are not 0, it will be considered that no analgesic was used on that day and following answers will be ignored.
- If answer to "Did you take any provided/prescribed analgesic for your endometriosis related pain?" is "No" and answer to question Ibuprofen intake is "Yes", but the number of Ibuprofen intakes is 0, it will be considered that no ibuprofen was used on that day. The same rule will be applied for narcotic analgesics.

Sponsor:	ObsEva		
Protocol:	19-OBE2109-005		
Document Version No.:	1.0	Document Date:	18-MAY-2021

Dyspareunia VRS Data:

- when question "Did you have any sexual intercourse?" is answered "No, I was not sexually active for reasons other than my endometriosis" or "No, I avoided sexual intercourse because of anticipation of pain" and there is an answer to question "How did your endometriosis related pain interfere with sexual intercourse?", only the "No" answer will be considered.
- when question "Did you have any sexual intercourse?" is blank and there is an answer to question "How did your endometriosis related pain interfere with sexual intercourse?", consider that "Yes" was answered to "Did you have any sexual intercourse".

#### HRUQ Data:

- when answer to triggering question 1 is "No" and at least one answer to question 2 to 6 (any answer different from 0) is present, ignore answer 2-6 in the analysis
- when answer to triggering question 7 is "No" and at least one answer to questions 8 to 9 (any answer different from 0) is present, ignore answers 8-9 in the analysis
- For questions 8-9, consider the number of times whatever the answer provided for "procedures" (ie if it is NO include number of times if different than 0)

#### HRPQ Data:

- When answer to question 9 is different than "endometriosis symptoms or its treatment(s) forced me to work part-time when I wanted to work full-time" and question 9bis is different than 0, ignore answer 9bis in the analysis.
- When answer to question 9 is different than "endometriosis symptoms or its treatment(s) kept me from having a job when I wanted to work full-time" and question 9ter is different than 0, ignore answer 9ter in the analysis.
- When answer to question 9 is different than "endometriosis symptoms or its treatment(s) kept me from having a job when I wanted to work part-time" and question 9quater is different than 0, ignore answer 9quater in the analysis

#### 4.2.9. **TVUS data**

If the depth recorded for a TVUS of uterus is 0 mm, the depth and the volume should be considered as missing (i.e., the assessment was done in 2 dimensions instead of 3 dimensions).

Sponsor:	ObsEva		
Protocol:	19-OBE2109-005		
Document Version No.:	1.0	Document Date:	18-MAY-2021

#### 4.2.10. Visit Windows

For all analyses except for the DXA assessments and the diary questionnaires, the visits as collected in the eCRF will be used.

All visit dates are calculated from the date the patient started treatment in the main study (Day 1 visit of 18-OBE2109-002 Edelweiss 2).

## DXA data

Visit windows rules for DXA assessments will be the following:

- The DXA assessment at Month 6 will be derived as the first non-missing DXA assessment with acceptable quality (accepted="Yes") and dated between Month 6 theoretical date (=Day 169) 28 days and Month 6 theoretical date + 28 days.
- The DXA assessment at Month 9 will be derived as the first non-missing DXA assessment with acceptable quality (accepted="Yes") and dated between Month 9 theoretical date (=Day 253) 28 days and Month 9 theoretical date + 28 days.
- The DXA assessment at Month 12 will be derived as the first non-missing DXA assessment with acceptable quality (accepted="Yes") and dated between Month 12 theoretical date (=Day 337 in the main study) -28 days and Month 12 theoretical date + 28 days.
- The DXA assessment at Month 6 Extension Follow-Up will be derived in the same way as the DXA assessment at Month 6. Theoretical date of Month 6 Extension Follow-up is 168 days after Month 12 theoretical date or after treatment discontinuation.

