10.2.1 Treatment Period

During the entire Treatment Period:

- the subject will use the same eDiary as during the main study. The eDiary should be completed daily, in the evening at approximately the same time, for use of provided/prescribed analgesics, uterine bleeding, pelvic pain, dyspareunia, dyschezia and daily function.
- the subject will take her daily dose of study medication at home except on the day of study visits where she will take her daily dose at site. There will be no IMP intake at the Month 12 visit. The last dose of study medication in this extension study will be the dose taken the day before Month 12 visit.
- the subject will be asked to bring her eDiary and her IMP kits at each visit to the site.
- the subject will receive contraception counselling at each visit.
- the subject will be provided/prescribed a limited quantity (as per Investigator's judgement) of standard doses of permitted analgesics as rescue medication for EAP for the duration of the study.
- the subject will receive calcium 500 to 1000 mg and vitamin D 400 IU supplementation which she will be advised to take daily (at least 4 hours from the intake of the study drug) until the end of the study. Intake should be recorded at each study visit in eCRF.
- AEs and concomitant medications will be recorded in the eCRF (excluding any provided/prescribed analgesics used for EAP will be recorded daily in the eDiary only).

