10.2.1.5 Study visit: Month 12 (Day 337 ± 3 days)

The following tests and evaluations will be performed :

- eDiary completion compliance check

- ePRO and ClinRO completion, ideally before any other procedures or assessments: EHP-30, EQ-5D-5L, PROMIS, mPGIS, PGIC, HRUQ, HRPQ, SSIQ andd PSIQ (mPGIS and PGIC must be completed last)
- Concomitant treatments recording
- AE recording
- Completion of the paper C-SSRS questionnaire (version for "already enrolled subjects" (see Appendix R) for patients responding to the C-SSRS for the first time during the study, or version "since last study visit" (see Appendix S) for patients for whom the C-SSRS was completed at the previous study visit)
- Final IMP accountability based on blisters
- ECG (at about the same time as but before the PK sample)
- Physical examination, including weight recording
- Vital signs (BP and heart rate)
- Urine pregnancy test
- Gynecological examination
- Manual breast examination (by palpation)
- TVUS of uterus
- Urinary protein dipstick
- Fasting (overnight) blood samples for haematology, coagulation parameters, chemistry, lipids, hormones (E2, LH, P4 and SHBG) and bone biomarkers
- PK sample (the time of dose administration on previous 4 days and time of PK sampling will be recorded)
- Endometrial biopsy, unless the endometrium thickness in TVUS is ≤ 5 mm, in which case no endometrial biopsy will be necessary (see section 10.4.5). Appropriate photo documentation of the endometrium thickness is mandatory.
- BMD assessed by DXA for femoral neck, hip and spine. DXA can be performed up to 10 days prior to the study visit which allows to get the DXA results ideally at the time of the Month 12 study visit at the latest.
- The subject will be verbally asked which treatment she believed she received during the Treatment Period in the extension study. The answer will be recorded in the eCRF.
- Contraception dispensing (if applicable) and counselling
- Prescribe/dispense permitted analgesics as rescue medication
- Dispense calcium and vitamin D supplementation

An additional question will be asked to the subject about the burden of filling in the eDiary (0 =not at all a burden, 10 = very much a burden). The answer will be recorded in the eCRF.

The Month 12 study visit constitutes the end of the Treatment Period pertaining to this extension study.

The subject will continue in the post-treatment 6-month Follow-Up (FU) Period.

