10.4.6 Bone mineral density and DXA

BMD of the femoral neck, total hip and lumbar spine will be assessed by DXA at the end of the Treatment Period (i.e. at Month 12 visit) and at the end of the Follow-Up Period (i.e. at Month 6 ExFU visit), under the supervision of a nominated primary technologist at the site. BMD for femoral neck, hip and spine will also be assessed at Month 9 for subjects who met the following criterion at any site on the Month 6 DXA scan: -2.5 < Z-score ≤ -1.5 .

A repeat DXA scan will be performed 6 months after the Follow-Up Period DXA for subjects with a BMD decrease from main study baseline > 1.5% for lumbar spine and/or > 2.5% for total hip.

For each subject, the same DXA machine must be used for all scan acquisitions.

All DXA scans will be read by a central imaging laboratory blinded to treatment group. There will also be centralized monitoring of DXA scan quality for each site including a pre-qualification phantom scan and a monthly review of daily quality control (QC) data.

In the event a scan does not meet quality standards, the site will be asked to repeat the scan. A repeated scan will be required for each scan showing 5% or more BMD loss from baseline.

Instructions to measure the BMD, detailed information on the centralized reading and QC and the stopping rules for subjects will be included in a specific imaging manual.

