## 4.8.3. Bone Mineral Density (BMD) by DXA

BMD of femoral neck, total hip and lumbar spine will be assessed by DXA at Baseline, Month 9 (if required) Month 12 and Month 6 of the extension follow-up (if required). Unacceptable DXA assessments (accepted="No") will not be summarized (hip, spine and femur considered separately).

In case of repeated values due to BMD loss ≥5%, the initial scan will be used in summaries. Initial and repeated scan values will be reported in the listings.

Calibrated values will be used if available, otherwise initial values will be considered.

BMD, expressed as both absolute values and Z-scores will be summarized at each visit in terms of actual values, changes from baseline, changes from baseline 2 (only for the subjects who are in the placebo arm in the main study) for each anatomic location. For absolute values only, percent change from baseline, percent changes from baseline 2 (only for the subjects who are in the placebo arm in the main study) and 95% confidence interval for the mean percent change from baseline and for the mean percent change from baseline 2 within each group will be produced at each time point.

The definition of both baselines are described in section 4.2.11.

Percent change from baseline and percent change from baseline 2 to Month 9, Month 12 and Month 6 extension follow-up will be described and will also be summarized in categories of percentage with the following classes:

- No change or increase,
- Decrease ≤ 3%,
- Decrease > 3% and  $\leq 5\%$ ,
- Decrease > 5% and  $\leq$  7%,
- Decrease > 7% and  $\leq$  8%,
- Decrease > 8%.

All data will be listed.

CRS-BS-TP-000005 V 1.0

Sponsor:	ObsEva		
Protocol:	19-OBE2109-00	5	
Document Version No.:	1.0	Document Date:	18-MAY-2021

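### DXA visit windows in the SAP do not consider time since last dose, so for a subject who stops soon after entry one off-drug follow-up scan can count as both Month 12 and Month 6 extension follow-up

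*SAP*

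**What the plan says.** SAP 4.2.10 takes DXA out of eCRF visit labelling: "For all analyses except for the DXA assessments and the diary questionnaires, the visits as collected in the eCRF will be used". For DXA it uses date windows instead. On Month 12 it says: "The DXA assessment at Month 12 will be derived as the first non-missing DXA assessment with acceptable quality", dated within 28 days either side of Day 337. The Month 9 rule has the same form around Day 253. The ExFU rule has the same form around a date that depends on the subject: "Theoretical date of Month 6 Extension Follow-up is 168 days after Month 12 theoretical date or after treatment discontinuation". None of these rules refers to the date of last dose, and none says that a scan may fill only one visit.

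The protocol gives the Month 12 scan a specific meaning. Under 10.4.6, BMD "will be assessed by DXA at the end of the Treatment Period (i.e. at Month 12 visit" and again at the end of follow-up. Under 10.7.2, a subject who withdraws during treatment has the Month 12 procedures, but without the DXA if she leaves before the Month 9 visit. Under 10.2.2.3, an early stopper's last follow-up visit, with its DXA, comes 168 ± 7 days after last intake, and the scan may be 10 days either side of that visit.

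SAP 4.8.3 adds one further selection rule. When a scan is repeated for a loss of 5% or more, "the initial scan will be used in summaries". That rule concerns repeats and does not consider treatment status.

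**The concern.** The Month 12 window is fixed in study time, while the ExFU window follows the subject's own stop date. For an early enough stop the two overlap, and the scan made to describe the state about six 28-day months after treatment also qualifies as the end-of-treatment scan.

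The protocol foresees such stops. Under 10.2.1.1, subjects may enter before all Month 6 results are back and must stop if a late result meets a discontinuation criterion. The Extension Safety Analysis Set, on which the BMD tables are run, keeps everyone who took at least one extension dose.

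BMD change is one of the six safety endpoints retained in SAP 2.5.3. SAP 4.8.3 plans by-visit means, a 95% confidence interval for the mean percent change, and categories of loss. A Month 12 row containing an off-drug value no longer describes the end of treatment, and the same value would appear again in the follow-up row. The SAP's own period definition (4.2.12) starts extension follow-up on the day after discontinuation, so by that definition the scan belongs to follow-up.

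**Working it through.** **Inputs.** Theoretical days come from SAP Table 3, window widths from SAP 4.2.10, and follow-up timing and tolerances from protocol 10.2.2.2 and 10.2.2.3. Let d be the day extension drug stops. I take d as both the last-intake date (protocol) and the treatment discontinuation date (SAP). The minus sign is missing in the text available to me for the lower limit at Month 6 and Month 9. I read it as ± 28 days, as printed for Month 12.

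**The plan's own days.** Day = 1 + 28 × month gives 169 for Month 6, 253 for Month 9 and 337 for Month 12. For a completer, ExFU is 337 + 168 = 505. All four match the documents.

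**Windows.**
- Month 9: 253 ± 28 = Days 225-281.
- Month 12: 337 ± 28 = Days 309-365.
- ExFU for an early stop: d + 168 ± 28 = d + 140 to d + 196.

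**Scheduled follow-up scan meeting both rules.**
- Nominal scan on d + 168. The condition d + 168 ≤ 365 gives d ≤ 197. A stop on Day 169 puts the scan on Day 337, and a stop on Day 197 puts it on Day 365. Stops on Days 169-197 are 29 days.
- Latest permitted scan (visit +7, DXA +10) on d + 185. The condition d + 185 ≤ 365 gives d ≤ 180. Up to Day 180 the scan lies in both windows whatever permitted date it takes: 12 stop days (169-180).
- Earliest permitted scan on d + 151. The condition d + 151 ≤ 365 gives d ≤ 214. Up to Day 214 a double label is possible: 46 stop days (169-214).
- Offsets of 151, 168 and 185 days all lie between 140 and 196, so the ExFU rule is also met.

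These counts are stop days, not subjects.

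**Less common route.** A subject who stops drug and later leaves follow-up at or after Month 3 ExFU is due a DXA 84 days or more off drug. The condition d + 84 ≤ 365 gives d ≤ 281, so for stops up to Day 281 such a scan can enter the Month 12 row. With the visit tolerance (77 days) the limit is Day 288. If the ± 10-day scan tolerance also applies (84 − 7 − 10 = 67 days), it is Day 298. The same rule can place such a scan in Month 9: a stop on Day 169 gives 169 + 84 = 253.

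**Other SAP rules.** The ± 14-day rules in 4.2.10 are for other safety data. They reach DXA only where external data labelled the scan as a main-study follow-up visit. They impose no condition on time since last dose.

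**Weight of one scan.** The documents give no achieved group sizes. Planned sizes are 288/3 = 96 per continuing group and 96/2 = 48 per placebo-switch group. If n subjects contribute to a row, one scan carries 1/n of the mean: about 1% at 96, 2% at 48, and 20% at an assumed n of 5. This is a weight, not an effect on BMD.

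**The case against.** A reader might make four stronger inferences that the documents do not support.

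- **Every stop on Days 169-197 is double counted.** That range holds at nominal timing only. With permitted tolerances the overlap is certain only up to Day 180. The SAP is also silent on whether a scan may fill two rows, so the text allows double use but does not prescribe it.
- **Early termination makes the problem frequent.** For this route it probably does the opposite. The subject must stop soon after entry and then remain in follow-up for about 168 days. SAP 2.5.3 and section 5 say the study ended prematurely and follow-up could not be completed for everyone, and 4.8.3 treats the follow-up scan as conditional. Individual early stops are the clearer source.
- **Withdrawal scans on Days 282-308 are wrongly lost.** They fall after the Month 9 window closes (Day 281) and before Month 12 opens (Day 309), so they enter no row. That is not an error. The endpoint is change at scheduled assessments, and Day 295, for example, is 42 days from both visits. Placing it in either would misstate exposure.
- **The Month 12 row is biased in a known direction.** The documents give no post-treatment BMD course from which to infer one.

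It is also fair to say that the analysis is descriptive, with no hypothesis tests, and that every scan can be inspected: "All data will be listed". These arguments lower the severity. They do not remove the overlap, because nothing in the SAP requires the Month 12 scan to be close to the last dose.

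**Conclusion.** The point holds, at minor severity. As written, SAP 4.2.10 lets a scheduled follow-up scan about 168 days off drug fill both the Month 12 and the ExFU rows for a subject who stops early, over the stop-day ranges shown above. Because no withdrawal DXA is required before Month 9, that scan would normally be her only one in Days 309-365, so the first-acceptable-scan rule would not displace it. A follow-up-withdrawal scan 84 days or more off drug can also enter the Month 12 row, but this needs two successive withdrawals.

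The conclusion rests on reading each window rule independently, as the text stands, and on equating the discontinuation date with the last dose. No stop dates are given, so the number of subjects and the direction of bias cannot be determined.

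**What to change.** Before unblinding, add to SAP 4.2.10:

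1. Each DXA scan fills one scheduled visit only.
2. For subjects who discontinued treatment before Month 12, a scan counts for Month 9 or Month 12 only if dated no later than the last extension dose plus a stated allowance. The allowance should be under 67 days, for example 28.
3. Later scans from these subjects can go only to Month 6 ExFU, under the existing 168-day rule.

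With 28 days, the latest scan accepted for Month 9 or Month 12 is d + 28. That is before the ExFU window opens (d + 140) and before the earliest follow-up-withdrawal scan (d + 67), so both routes are closed. Withdrawal scans keep their place, including those taken ahead of the visit, since "DXA can be performed up to 10 days prior to the study visit" and the rule sets no lower limit relative to last dose. The 4.8.3 rule on repeated scans is unchanged.

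Leave completers' windows alone. On last dose the protocol says: "The last dose of study medication in this extension study will be the dose taken the day before Month 12 visit". A completer seen on Day 334 (337 − 3) therefore has her last dose on Day 333. A 28-day limit would end at 333 + 28 = Day 361 and drop scans on Days 362-365 that are accepted now.

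The cost is a few lines of SAP text and no new data. The allowance is a choice that must be stated in advance. Follow-up-withdrawal scans taken after the allowance but before d + 140 would appear in the listing only. A separate end-of-treatment row, which would also show scans from Days 282-308, is optional. It would mix exposure times and repeat scans already shown at Month 9 or Month 12.
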